**Protocol title: Non-invasive Evaluation of Portal
Hypertension in Patients With Compensated
Advanced Chronic Liver Disease by Liver Stiffness
Measurement Using Liver Incytes**

PI: [name]

NCT04576897

Document Date: August 5, 2021

Non-invasive Evaluation of Portal Hypertension in Patients with Compensated Advanced Chronic Liver Disease by Liver Stiffness Measurement Using Velacur

Principal Investigator
[name]

Co-Investigators

[name]

[name]

[name]

[name], PAC

[name], PAC

[name], BS, RRT

Division of Gastroenterology and Hepatology

Indiana University School of Medicine

Indianapolis, Indiana

USA

Address:

[name]

[name]

Email: [contact]

[contact]

[contact]

Study Design: Prospective Observational Study

Number of Patients: 200 patients with compensated cirrhosis

1. Introduction:

For long, cirrhosis has been considered as end-stage liver disease but it is increasingly being realized that the 1-year mortality in cirrhosis varies widely, from 1% to 57%, depending on the occurrence of clinical decompensating events.¹ Histopathologists have proposed that the histological term cirrhosis should be substituted by advanced liver disease, to underline the dynamic processes and variable prognosis of the disorder.² A new term, compensated advanced chronic liver disease (cACLD) defining patients in the early phases of severe chronic liver disease, including both patients with severe fibrosis or pre-cirrhotic patients and patients with compensated cirrhosis is considered very helpful for both clinical practice and research purposes. Cirrhosis should no longer be regarded as a terminal disease and the concept of a dynamic process is increasingly accepted. A prognostic clinical subclassification with four distinct stages has been proposed with substantially differing likelihoods of mortality (Figure 1).

Currently, the management of patients with cACLD includes assessment for severity of portal hypertension and risk stratification. Cirrhosis is currently classified into two main prognostic stages: compensated and decompensated cirrhosis.^{1, 3} This classification depends on the presence or absence of clinically evident decompensating events (specifically ascites, variceal hemorrhage, and encephalopathy), with a median survival in the compensated stage that exceeds 12 years, while it is only 1.8 years in patients who develop decompensation (Figure).³

Figure. Stages of compensated advanced chronic liver disease and liver-related clinical events

Advanced Liver Disease					
	Compensated Advanced Chronic Liver Disease			Decompensated Cirrhosis	
	Advanced Fibrosis	Compensated Cirrhosis			
Stage	F3-F4	Stage 1	Stage 2	Stage 3	Stage 4
Clinical Manifestations	No varices	No varices	Varices	Ascites ± Varices	Bleeding ± Ascites
No ascites	No ascites	No ascites	No ascites		
Liver-related mortality	Less likely	1%	3%	20%	57%
Risk of HCC	Very Low			3% per year	
Time-interval	1/3 rd progress over 3-4 yrs		? Rate of progression →		

The Child-Turcotte-Pugh (CTP) classification has been used to stratify patients with cirrhosis.⁴ Patients with cirrhosis belonging to the CTP-A class are compensated, whereas those in the CTP-B/C class are mostly decompensated.⁴ Similarly, Model for End-Stage Liver Disease (MELD) is a reliable measure of mortality risk in patients with end-stage liver disease and used to help prioritize organ allocation for transplant.^{5, 6} However, MELD scores of <10, typically seen in CTP-A, are unlikely to have prognostic value as the likelihood of clinical events in a 1 to 2-year

time frame is low.^{1, 7, 8} Therefore, both CTP and MELD scores best stratify cirrhosis patients with decompensation and have limited use in compensated cirrhotics who have no liver-related symptoms.

Patients with compensated cirrhosis are substaged based on the severity of portal hypertension (Figure 1).⁹ However, measurement of portal pressure through direct puncture of the portal vein is risky and not routinely performed. Therefore, portal pressure is assessed indirectly by calculation of hepatic vein pressure gradient (HVPG) by measuring the difference between wedge and free hepatic venous pressure.¹⁰⁻¹² The normal value of HVPG is between 3 and 5 mmHg.^{11, 12} Currently, the severity of portal hypertension is defined as mild when HVPG is ≥ 6 but <10 mm Hg, ≥ 10 mm Hg as clinically significant portal hypertension (CSPH), and ≥ 12 mm Hg as severe portal hypertension (SPH).¹³ Evaluation of a compensated cirrhotic by HVPG is ideal for risk stratification as CSPH is associated with an increased risk of varices, decompensation (ascites, variceal hemorrhage and/or hepatic encephalopathy) and hepatocellular cancer.¹⁴⁻¹⁶ However, measurement of HVPG is cumbersome, invasive, non-standardized and often limited to tertiary care centers due to limited expertise.¹⁷ Therefore, there is a need for non-invasive tools that can estimate HVPG easily, reproducibly and with high diagnostic accuracy. It is thus not a surprise that some investigators have examined the prognostic value of AST-to-Platelets Ratio Index (APRI) and fibrosis-4 (FIB-4) for prediction of adverse clinical outcomes related to portal hypertension.^{18, 19}

Liver stiffness measurement (LSM) by vibration controlled transient elastography (VCTE) is currently used for non-invasive diagnosis liver fibrosis in patients with chronic liver disease. In patients with cirrhosis, LSM is likely indicative of cumulative stiffness from underlying liver fibrosis and portal hypertension. In addition, some studies have reported a good correlation between LSM and HVPG and its ability to detect CSPH.^{20, 21} In fact, in the recent Baveno conference (Baveno VI), a screening endoscopy was not recommended in patients with LSM <20 kilopascals (kPa) and platelet count $>150,000/\mu\text{l}$ due to very low risk of having varices at high risk of bleeding.^{21, 22} In one study that examined the prognostic accuracy of HVPG and serum fibrosis biomarkers, both measures worked equally well in predicting clinical outcomes.¹⁹

FibroScan® is a commonly used diagnostic device based on VCTE.^{23, 24} While the use of FibroScan® in liver clinics is attractive as a point of care exam that can provide immediate indirect data about hepatic steatosis and fibrosis in the clinic, advancement in quantitative ultrasound technology may now allow even more detailed and directed non-invasive assessment of these measures of liver disease.

Velacur offers the ability to simultaneously and non-invasively measure Attenuation Coefficient Estimate (ACE) as a quantitative measure of ultrasound attenuation²⁵ and detection of hepatic steatosis in addition to LSM which measures deep volumetric liver elasticity using steady state shear waves, known as shear wave absolute vibroelastography (SWAVE). This technology enables measurements of liver elasticity to a depth equal to the B-mode image, or in excess of 15 cm. The system consists of an ultrasound machine, a vibration device to excite shear waves in the patient and an ultrasound transducer. The vibration device induces shear waves in the liver at four different frequencies between 40Hz and 70Hz simultaneously. The ultrasound volume is acquired through the ribs at the same location as a typical transient elastography (TE) measurement. Volumes are collected in a fan of approximately 15 degrees and taken at a depth up to 15cm, which is much deeper than Fibroscan® measurement (6 cm), and allows for much larger sample measurement (100,000 mm³) versus that measured by Fibroscan® (3,140 mm³).

The natural history of chronic liver disease with advanced fibrosis/ cirrhosis across the different clinical stages of cirrhosis (Figure) is currently not well understood. Therefore, non-invasive tools that can assess the severity of cirrhosis and risk stratify prior to decompensation is currently an unmet need. The assessment of LSM using Velacur may eventually allow for a noninvasive, immediate, objective and efficient method for estimation of disease severity in patients with cirrhosis. Moreover, assessment over time of LSM may also allow for assessment of disease progression or regression from treatment interventions. We anticipate that baseline measurements of LSM and longitudinal changes (Δ LSM/ Δ t) will serve as a prognostic tool in patients with cACLD.

Hypothesis: The severity of portal hypertension in compensated advanced chronic liver disease (cACLD) can be assessed measuring LSM by Velacur.

Specific Aim 1: To examine the relationship between LSM by Velacur and the presence of esophageal or gastric varices and portal hypertensive gastropathy in patients with compensated

advanced chronic liver disease (cACLD). We will measure LSM by Velacur in this single center clinical study comprising of 200 patients with cACLD (defined by LSM ≥ 10 kilopascals (kPa) according to the Baveno VI recommendations) who have not had a liver transplant.

Specific Aim 2: Compare the performance of LSM by Velacur for predicting CSPH, esophageal and gastric varices to that of FibroScan® and other non-invasive markers such as MELD, CPT, platelets count, splenomegaly, APRI and FIB4.

Proposed Study Design: This is a cross sectional study that evaluates the relationship between LSM by Velacur in patients with cACLD and manifestations of portal hypertension.

Inclusion/Exclusion Criteria

Inclusion criteria:

1. Adults aged 18 years or older
2. Ability to provide informed consent
3. Diagnosis of cirrhosis based on liver biopsy, imaging, FibroScan®, or Hepatologist assessment.
4. Planned or recommendation of one of the following:
 - a. standard of care upper endoscopy to screen for varices within (+/-) 6 months of the Velacur study
 - b. standard of care transjugular liver biopsy with portal pressure measurement within (+/-) 6 months of the Velacur study

Exclusion criteria:

1. Inability or refusal to provide informed consent
2. Fasting for less than three hours prior to the scan
3. Subject is a pregnant or lactating female
4. Current, significant alcohol consumption
5. Subject is unable to reliably quantify alcohol consumption based upon local study physician judgment
6. Patients with a pacemaker or defibrillator
7. Acute hepatitis defined as AST/ALT > 500 U/L
8. Ascites

Screening and Enrollment

Up to 200 patients with cACLD who have not undergone liver transplantation who are seen in the liver clinics at IUH-Digestive and Liver Disorder Clinics and at Springmill Clinic will be enrolled into this prospective cross sectional study after obtaining informed consent. Standard inclusion and exclusion criteria for Velacur will be used. Patients who meet the inclusion criteria will be offered the opportunity to undergo additional testing with Velacur to measure LSM after informed consent. In addition to history and physical, we will capture pre-specified liver related findings using standardized case report forms. Participants will be enrolled over a 24 month period.

Study Procedures

At Enrollment: After subject identification, an informed consent will be obtained. All patients have to be fasting for at least three hours prior to performance of the study. Velacur exam will be performed by a Velacur certified technician. Duration of participation for the subject should be no more than one hour. Medical information from the subjects, including results of the scans, historical laboratory and diagnostic testing data will be obtained from medical records and will be entered into a database. Laboratory data for calculating non-invasive markers such as MELD, CPT, platelets count, splenomegaly, APRI and FIB4 will be collected from standard of care labs done within 6 months of the endoscopy or portal pressure measurement by transjugular liver biopsy.

Reporting of Adverse Events or Unanticipated Problems Involving Risk to Participants or Others

The Division of Gastroenterology/Hepatology at IUSM has considerable experience in the conduct of clinical studies.

Participation in this study may cause a loss of privacy. To minimize this risk, all of the patient's personal and medical data will be considered confidential to the extent allowed by law; every effort will be made to keep all of the information strictly confidential. All study information will be stored in locked cabinets and on password-protected computers. Only authorized personnel will have

access to the samples, databases, and results. When the study is published, no names or other identifying information will be used.

While there are no direct risks from use of Velacur, patients may be uncomfortable lying on their back for a brief period of time. They may experience soreness at the probe site. There is a small risk of an allergic reaction to the gel utilized during the procedure.

Patients will be closely monitored for any evidence of adverse events. Any adverse events associated with the study will be documented and the IRB will be notified per reporting guidelines.

Study Withdrawal/Discontinuation

The subject is free to withdraw from the study for any reason and at any time without giving a reason for doing so and without penalty or prejudice. The Investigator is also free to terminate a subject's involvement in the study at any time if the subject's clinical condition warrants it.

Statistical Considerations

Descriptive statistics such as mean, standard error, and percentages were used to characterize the cohort. Comparisons will be made between groups by using Student t test or analysis of variance. Pearson correlation coefficient will be used to detect the correlation between continuous variables. Multivariate analysis will be performed to examine the independent association between dependent and several independent variables. The diagnostic accuracy of LSM will be calculated using area under the receiver operator curve analysis. Sample size is based on clinical experience and precedent established for studies of similar design.

Privacy/Confidentiality Issues

Participation in this study may cause a loss of privacy. To minimize this risk, all of the patient's personal and medical data will be considered confidential to the extent allowed by law; every effort will be made to keep all of the information strictly confidential. All study information will be stored in locked cabinets and on password-protected computers. Only authorized personnel will have access to the samples, databases, and results. Samples will be labeled with a code. When the study is published, no names or other identifying information will be used.

Follow-up and Record Retention

Use of Velacur is an additional tool for diagnostic purposes and provides physicians with additional clinical information to optimize patient care. No direct follow-up with participants is planned. However, the patients may be approached for repeat study and with informed consent may be enrolled again to measure any changes in the LSM and SS that may occur over time. Study records and documents will be maintained in accordance with federal, state, and university laws.

References:

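### The cohort is to be described by mean and standard error, which does not show patient spread; Welch tests would be a cheap secondary safeguard for the group comparisons (minor)

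*Protocol*

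**What the plan says.** The protocol's Statistical Considerations section and the SAP carry the same short paragraph. On description: "Descriptive statistics such as mean, standard error, and percentages were used to characterize the cohort". On group comparison: "Comparisons will be made between groups by using Student t test or analysis of variance". Neither document names SD, median, IQR or range. Neither mentions a variance check, a Welch or rank-based test, or a transformation.

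That paragraph does not name the groups. Specific Aim 1 suggests them: "To examine the relationship between LSM by Velacur and the presence of esophageal or gastric varices and portal hypertensive gastropathy". The design is one cross-sectional cohort ("This is a cross sectional study that evaluates the relationship between LSM by Velacur in patients with cACLD and manifestations of portal hypertension") with no quota for any group. Enrolment is "Up to 200 patients with cACLD who have not undergone liver transplantation", and the basis given for that number is: "Sample size is based on clinical experience and precedent established for studies of similar design". No alpha, SD, prevalence of varices or effect size is stated.

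**The concern.** **Description.** The stated purpose is to characterize the cohort, and the only spread-like statistic named is one that shrinks as n grows. A reader who takes mean ± SE as a picture of the patients will think them far more alike than they are. Two equally varied sets of measurements will also look different if their n differs. SD can be recovered from SE, but only where n is printed for that variable.

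**Comparison.** Student's t test and ordinary analysis of variance, as usually understood, pool the variance across groups. With similar group sizes this does little harm even if variances differ. Here nothing in the design makes the sizes similar, because they depend on what endoscopy finds. If the spread of liver stiffness also differs between patients with and without varices, the p-values would be off, in a direction set by which group is the more variable.

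**Working it through.** **Inputs from the documents.** N is up to 200 (Screening and Enrollment); the summaries and tests are those quoted above. The figure of 200 cannot be reproduced, because no input to a sample-size formula is given. **Everything else below is assumed:** SDs, SD ratios, group splits, number of groups, a two-sided nominal level of 5%, the 0.4 SD difference and the lognormal shape.

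**1. SE against SD.** SE = SD/√n, and √200 = 14.14. An assumed SD of 15 would print as:
- n = 200: 15/14.14 = 1.1
- n = 60: 15/7.75 = 1.9
- n = 30: 15/5.48 = 2.7

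The patients are equally varied in all three lines; only n changes.

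**2. Student's t with unequal variances.** In large samples the actual level is 2Φ(−1.96·√(A/B)), where
- A = pooled variance × (1/n₁ + 1/n₂), the variance the test uses;
- B = s₁²/n₁ + s₂²/n₂, the true variance of the difference.

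Example with 60 vs 140 and the smaller group at twice the SD. Pooled variance = (59×4 + 139×1)/198 = 1.894. A = 1.894 × 0.02381 = 0.0451. B = 4/60 + 1/140 = 0.0738. A/B = 0.611, and the level is 2Φ(−1.53) = 12.6%.

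The same formula over a range of SD ratios at 60 vs 140:

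| SD ratio | Smaller group more variable | Larger group more variable |
|---|---|---|
| 1.0 | 5.0% | 5.0% |
| 1.1 | 5.9% | 4.2% |
| 1.2 | 6.8% | 3.5% |
| 1.5 | 9.4% | 2.2% |
| 2.0 | 12.6% | 1.2% |

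Simulation with normal data and equal means agrees: 9.3% and 12.6% at ratios 1.5 and 2, and 2.3% and 1.3% reversed. Welch's t gives 4.9% to 5.1%. Other splits at ratios 1.5 and 2, with the smaller group more variable:
- 80 vs 120: 7.0% and 8.4%
- 40 vs 160: 12.1% and 17.8%
- 100 vs 100: 5.0% to 5.1%

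**3. Three groups of 100/60/40, normal data.** With SDs of 1/1.25/1.5 and 1/1.5/2 (smallest group most variable), analysis of variance runs at 8.2% and 10.8%. With the order reversed it runs at 3.1% and 2.5%. Welch's version gives 4.9% to 5.0%. With groups of 67/67/66, ordinary analysis of variance gives 5.2% to 5.6%.

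**4. Skewed data.** Lognormal, equal means, log-SD 0.7 in the larger group, and the smaller group with 1.5 to 2 times the SD. At 60 vs 140, Student runs at about 9% to 12% and Welch at about 7% to 9%. At 30 vs 170, Student runs at about 12% to 19% and Welch at about 9% to 13%. If the same lognormal holds in every group, Welch's t runs at 5.4% (60 vs 140) and Welch's analysis of variance at 5.6% (100/60/40), against 4.9% and 4.7% for the pooled tests.

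**5. Power cost when variances are equal** (true difference 0.4 SD), Welch against Student:
- 60 vs 140: 72.8% against 73.2%
- 30 vs 170: 50.5% against 52.0%

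**The case against.** **On description.** The list is introduced as examples, so SD and quantiles are not ruled out. A labelled SE can be converted if n is printed. Nor will n vary for everything: the Velacur measurement is taken at enrolment in all participants. The two entry routes under inclusion item 4 ("Planned or recommendation of one of the following") bear mainly on portal pressure, which only the transjugular route is sure to supply. Gaps in the standard-of-care records could make n differ for laboratory values, but the documents do not say so. All of this stands, and it keeps the point a reporting matter. It does not make SE a suitable description of a cohort.

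**On the tests.** A reader might infer that unequal group sizes alone invalidate Student's t test or analysis of variance. They do not: with equal SDs the level stays at 5% for any split. Unequal variances are needed as well, and the documents give no evidence of them. The stiffness floor of 10 kPa in Aim 1 makes skew and unequal spread plausible but does not show them. With mild differences in SD the distortion is about one or two percentage points.

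A reader might also infer that Welch's test guarantees 5%. Step 4 shows that it does not under skew combined with unequal variance; it only does better than Student.

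Finally, preferring Welch by default is partly a matter of practice in a short plan for an observational study. These comparisons are not designated primary. That stands too, and is why this half is only a suggestion.

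**Conclusion.** The descriptive statistic is wrong for its stated purpose in both documents. The understatement of spread is exact arithmetic: a factor of √n, or 14.1 at n = 200. It affects presentation only.

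The change of tests is a sound, cheap improvement but not the correction of a demonstrated error. Its possible benefit at 60 vs 140 is to avoid a level of about 6% to 13%, or one well below 5% in the other direction. That benefit depends on variances and group sizes both differing, neither of which the documents establish, so the size and direction of any actual error are unknown.

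The documents do not support a claim that the study's accuracy results are at risk. Diagnostic accuracy is to be assessed by the area under the ROC curve, and the empirical estimate depends neither on the descriptive summary nor on equal variances. Severity: minor.

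**What to change.** Make both edits in the protocol and the SAP.

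1. Describe continuous variables by mean and SD, or by median and IQR if skewed, with n for each variable. Keep SE or confidence intervals for estimates such as mean differences and areas under the curve. This costs nothing beyond wording; reported spread will look wider.

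2. As a secondary improvement, name the groups to be compared. Use Welch's t test for two groups and Welch's analysis of variance for more than two, on a log scale if a variable is clearly skewed. Fixing this before analysis also avoids a choice between tests after the p-values are seen.

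The second edit costs 0.4 to 1.5 percentage points of power in the equal-variance cases above, and a slight excess over 5% under strong skew shared by all groups. Some p-values may move in either direction. A log-scale comparison concerns geometric rather than arithmetic means, and the report should say so.

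### For LSM against HVPG as continuous measures the plan names only a Pearson correlation, which shows neither the error in mmHg nor how often the severity grade would be wrong

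*Protocol*

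**What the plan says.** The hypothesis in the Protocol is "The severity of portal hypertension in compensated advanced chronic liver disease (cACLD) can be assessed measuring LSM by Velacur". The Introduction grades severity by HVPG. A severe category starts at 12 mmHg, and the grades below it are given as "mild when HVPG is ≥ 6 but <10 mm Hg, ≥ 10 mm Hg as clinically significant portal hypertension (CSPH". It also states a general need: "there is a need for non-invasive tools that can estimate HVPG easily, reproducibly and with high diagnostic accuracy".

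The numbered aims are narrower. Specific Aim 1 is "To examine the relationship between LSM by Velacur and the presence of esophageal or gastric varices and portal hypertensive gastropathy". Specific Aim 2 is "Compare the performance of LSM by Velacur for predicting CSPH, esophageal and gastric varices to that of FibroScan" and a list of other markers.

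The Statistical Considerations, identical in Protocol and SAP, name a t test or ANOVA for group comparisons, a multivariate analysis with no outcome named, and two methods that bear on this point:

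- For continuous measures: "Pearson correlation coefficient will be used to detect the correlation between continuous variables"
- For accuracy: "The diagnostic accuracy of LSM will be calculated using area under the receiver operator curve analysis"

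Neither document names a model from LSM to HVPG, a prediction error, a calibration check, or a cross-table of predicted against measured grade.

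**The concern.** Some patients enter through transjugular biopsy with portal pressure measurement (Inclusion criterion 4b), so paired LSM and HVPG values will exist. If severity means HVPG grade, two questions follow from the hypothesis: how far off is the HVPG implied by a given LSM, and how often is the grade wrong?

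A Pearson coefficient answers neither. It has no units, and it depends on how widely HVPG is spread among the patients sent for biopsy, so it describes the sample as well as the device. AUROC answers a different question. It measures how well LSM ranks patients above and below a single cut, and says nothing about mmHg error, calibration or placement across grades.

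At stake is what the study can say about severity. A respectable r could be reported while individual estimates remain wider than the grades they are meant to separate, and the planned output would not show this.

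**Working it through.** The plan gives no correlation, AUROC or error rate, so it has no figure of its own to reproduce. The check asks what a given r would imply.

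**Inputs**

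- From the Introduction: cut-offs at 6, 10 and 12 mmHg. Used as exclusive bands these give <6, 6 to <10, 10 to <12, and 12 or more. The two inner bands are 4 and 2 mmHg wide.
- Assumed, because the documents give none: HVPG mean 8 to 14 mmHg, SD 4 to 6 mmHg, r = 0.7 and 0.9, bivariate normal data, and LSM converted to HVPG by the ideal regression line.

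**Step 1: error in mmHg.** The 95% prediction half-width is 1.96 × SD × √(1 − r²), ignoring the uncertainty of the fitted line.

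- r = 0.7, SD 4: 1.96 × 4 × √0.51 = 5.6. SD 6: 1.96 × 6 × √0.51 = 8.4.
- r = 0.9, SD 4: 1.96 × 4 × √0.19 = 3.4. SD 6: 1.96 × 6 × √0.19 = 5.1.

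Even the smallest of these gives a full interval of 2 × 3.4 = 6.8 mmHg, wider than either inner band.

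**Step 2: share misplaced.** Predicted HVPG is normal with the same mean and SD r × SD. Measured HVPG around it has SD equal to SD × √(1 − r²). The wrong-grade share is one minus the probability that predicted and measured values fall in the same band, integrated numerically. Ranges below run over SD 4 to 6.

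| Assumed mean HVPG (mmHg) | Wrong grade, r = 0.7 | Wrong grade, r = 0.9 | Wrong side of 10, r = 0.7 | Wrong side of 10, r = 0.9 |
|---|---|---|---|---|
| 8 | 48.7–50.5% | 31.8–33.5% | 21.6–23.6% | 12.6–13.5% |
| 10 | 50.9–51.6% | 33.1–34.0% | 25.3% | 14.4% |
| 12 | 44.0–45.9% | 29.1–31.1% | 21.6–23.6% | 12.6–13.5% |
| 14 | 30.1–36.7% | 21.0–25.9% | 13.5–19.1% | 8.4–11.3% |

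At mean 10 the share on the wrong side of 10 has the closed form arccos(r)/π: 0.795/3.142 = 0.253 at r = 0.7 and 0.451/3.142 = 0.144 at r = 0.9, which agrees with the table.

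**Step 3: dependence of r on spread.** Hold the residual SD at 3 mmHg (assumption). Then r = √(1 − 9/SD²), which is 0.66, 0.80 and 0.87 for HVPG SDs of 4, 5 and 6. The device error is the same in all three cases, but the correlation is not.

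**Step 4: what AUROC would show.** Under the same model with mean 10 or 12, the AUROC for CSPH is about 0.83 at r = 0.7 and about 0.88 at r = 0.8. That is real information about the 10 mmHg cut, but it carries neither the mmHg error nor the grade error.

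**Step 5: precision.** The number of patients with HVPG is not stated. By Fisher's transformation, tanh(arctanh 0.7 ± 1.96/√(n − 3)), an observed r of 0.7 has a 95% interval of 0.37 to 0.87 with 20 patients and 0.62 to 0.76 with 200.

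**The case against.** The strongest reply is that the study does not set out to estimate HVPG. That need is stated as background. The targets in both aims are presence-or-absence states, for which AUROC is a natural and planned analysis. The hypothesis says that severity can be assessed; it does not promise a value in mmHg. The Pearson sentence does not mention HVPG, and nothing makes r a criterion of success. The four exclusive bands are a reading of the protocol's definitions, in which severe is nested within CSPH, and narrow bands raise disagreement. At the CSPH cut, the one HVPG threshold the aims use, misplacement is much lower.

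Most of this stands, and it limits the point. A reader might infer that the plan evaluates LSM by correlation alone. It does not: AUROC, group comparisons and a multivariate analysis are in the same paragraph. A reader might also infer that a high correlation would leave about half of patients in the wrong grade. That holds only near r = 0.7 with an assumed mean HVPG of 8 to 10 mmHg; at r = 0.9 it is a third or less.

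What the reply does not remove is the gap for severity. The hypothesis uses that word, the protocol's grading of portal hypertension severity is by HVPG, and no listed method reports error on that scale.

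**Conclusion.** The point holds for LSM against HVPG as continuous measures, and only there. The plan's tool for that comparison is a correlation, and AUROC covers CSPH yes/no without filling the gap. Over assumed means of 8 to 14 and SDs of 4 to 6 mmHg:

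- r = 0.7: half-width 5.6 to 8.4 mmHg, about 30 to 52% in the wrong grade, about 14 to 25% on the wrong side of 10 mmHg.
- r = 0.9: half-width 3.4 to 5.1 mmHg, about 21 to 34% in the wrong grade, about 8 to 14% on the wrong side of 10 mmHg.

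These figures rest on normality, a linear relation and ideal calibration. The mean, SD and r are not in the documents. This is an improvement the plan should make for its severity hypothesis. It does not undermine the analyses for the numbered aims.

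**What to change.** Add to the Statistical Considerations of both documents that, in patients with measured HVPG:

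- HVPG will be regressed on Velacur LSM, allowing for curvature if the numbers permit, and the 95% prediction interval reported in mmHg.
- A cross-validated table of predicted against measured protocol grade will be given, stating whether severe is counted as a separate band or within CSPH.
- The same figures will be given for FibroScan in patients who have both scans. Study Procedures schedules only the Velacur exam, so this pairing cannot be assumed for everyone.
- Pearson r will be reported as descriptive only, and any statement about estimating HVPG or its grade will rest on the prediction interval and the table.

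State the number of patients with HVPG, and label the analysis exploratory if it is small, since a curved fit and a four-grade table may then be unstable.

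The cost is a short addition to the plan and a little more analysis, with no new procedures. The reported precision will look less favourable than a correlation coefficient.

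### Does the single AUC sentence leave the CSPH part of Aim 2 without a usable reference standard or analysis set?

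*Protocol*

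**What the plan says.** Specific Aim 1 describes the study as one cohort: "We will measure LSM by Velacur in this single center clinical study comprising of 200 patients with cACLD". Screening and Enrollment gives 200 as an upper limit on enrolment. Specific Aim 2 sets the comparison: "Compare the performance of LSM by Velacur for predicting CSPH, esophageal and gastric varices to that of FibroScan" and six further named markers.

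The Introduction defines CSPH as an HVPG of at least 10 mm Hg. Inclusion criterion 4 reads "Planned or recommendation of one of the following", then lists a standard-of-care screening endoscopy (4a) and a standard-of-care transjugular biopsy with pressure measurement (4b), each within six months either side of the Velacur scan. The study itself adds no pressure measurement.

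On analysis, Statistical Considerations in both documents offers "The diagnostic accuracy of LSM will be calculated using area under the receiver operator curve analysis" and, for size, "Sample size is based on clinical experience and precedent established for studies of similar design".

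On data, Screening and Enrollment says "we will capture pre-specified liver related findings using standardized case report forms", and Study Procedures takes scan, laboratory and diagnostic results from medical records. Follow-up and Record Retention adds "No direct follow-up with participants is planned".

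**The concern.** Aim 2 has several targets and the cohort has two entry routes, yet one sentence covers accuracy. CSPH needs HVPG, and HVPG will exist only where a clinician ordered it. The Introduction itself calls the test invasive and often confined to tertiary centres. A patient entering by 4a may never have it, a patient entering by 4b may have no endoscopy, and a mere recommendation could leave a patient with neither result.

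Three things appear to be at stake. First, a reader might attach a CSPH result to the whole cohort of up to 200 when it comes from far fewer. Second, patients sent for pressure measurement may be unrepresentative. Velacur is offered only after eligibility ("Patients who meet the inclusion criteria will be offered the opportunity to undergo additional testing with Velacur to measure LSM"), so referral may depend on the very markers it is compared with, which could tilt the comparison. Third, with no direct follow-up, results of procedures done after the scan might be missed.

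**Working it through.** **1. Which reference test serves which target.** Set side by side, the documents already supply the link:

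| Target | Reference test | Threshold and window |
|---|---|---|
| CSPH | HVPG | at least 10 mm Hg (Introduction); ±6 months (criterion 4b) |
| Varices, gastropathy | Upper endoscopy | ±6 months (criterion 4a) |

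No other CSPH reference is offered. Varices are described as associated with CSPH, not as a stand-in for it. The HVPG restriction therefore applies to the CSPH part of Aim 2 only; the varices comparison uses patients with endoscopy.

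**2. Precision.** The plan gives no expected AUC, prevalence, precision, alpha or power, so there is no figure to reproduce. All inputs below are assumptions. The Hanley-McNeil variance for AUC A, with n1 patients with CSPH and n0 without, is

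Var = [A(1−A) + (n1−1)(a−A²) + (n0−1)(b−A²)] / (n1·n0), where a = A/(2−A) and b = 2A²/(1+A).

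For A = 0.80 and n1 = n0 = 100: a = 0.6667, b = 0.7111, A² = 0.64. The numerator is 0.16 + 99 × 0.0267 + 99 × 0.0711 = 9.84. Var = 9.84/10,000 = 0.000984, SE = 0.0314, and the half-width (1.96 SE) is 0.061.

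For paired AUCs, SE² = SE1² + SE2² − 2r·SE1·SE2, where r is the correlation of the two estimates. Power is for 0.85 against 0.75, two-sided 5%.

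| Patients with HVPG | Half-width, AUC 0.80, 50% CSPH | Range over AUC 0.75–0.85, CSPH 30–70% | Paired power, r = 0.5, 50% CSPH | Range over r 0.3–0.7, CSPH 30–70% |
|---|---|---|---|---|
| 200 | 0.061 | 0.052–0.079 | 89% | 63–98% |
| 100 | 0.087 | 0.074–0.112 | 61% | 36–81% |
| 50 | 0.124 | 0.105–0.159 | 35% | 20–51% |
| 20 | 0.200 | 0.171–0.255 | 16% | 11–24% |

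A half-width of 0.10 at AUC 0.80 and 50% CSPH needs 77 patients with HVPG, which is 77/200 = 39% of full enrolment (55 to 125 over the same ranges of AUC and CSPH). So the number with HVPG matters for precision, but the plan states no target for it to miss.

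**3. Referral on a comparator.** A binormal simulation took two markers with equal true AUC 0.80, 50% CSPH, within-class correlation 0.3 to 0.7, and selection on the comparator alone. The apparent Velacur advantage was:

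- referral rising (10% to 40%) or falling (40% to 10%) steadily with the comparator: 0.001 to 0.007;
- lowest third of the comparator never referred: 0.013 to 0.047;
- referral concentrated in the middle third: 0.025 to 0.070;
- referral concentrated in the outer thirds: −0.021 to −0.001.

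For scale, the paired half-width when both AUCs are 0.80 is the single half-width times √(2(1−r)). With 200 patients this is 0.0615 × √0.6 = 0.048 at r = 0.7 and 0.0615 × √1.4 = 0.073 at r = 0.3. Steady referral is well inside that. The larger values need hard cut-offs or middle-third referral, and the documents describe neither for pressure measurement. The rule in the Introduction (stiffness below 20 kPa with platelets above 150,000) concerns screening endoscopy. It would act mainly on who enters by 4a, not on who is verified by HVPG.

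**4. Capture of results.** Criterion 4 accepts a procedure up to six months after the scan, and Study Procedures times the laboratory data from the date of the endoscopy or pressure measurement. Both presuppose that the procedure's date and result are collected. Ruling out direct follow-up of participants does not rule out reading their records.

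**The case for a change.** The strongest case for a change is that excluding unverified patients by default does not tell the reader how many patients the CSPH analysis will hold, how precise it will be, on which common set markers are compared, or to whom the result applies. Criterion 4 names the tests as entry routes and never ties them to a target in the analysis. Whether the CSPH comparison can succeed depends on a number the plan never gives: with r = 0.5 and 50% CSPH, power falls from 89% at 200 to 35% at 50. A few sentences would close the gap.

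Most of this stands as a description. The number with HVPG is unknown, and the SAP adds nothing to the Protocol. It is weaker as a reason to amend. The set, the threshold and the window follow from text already present. All markers are measured in the same patients, so a paired comparison is the natural analysis. The number verified and the interval appear with any competently reported AUC. An expected number per target would need site referral data that the documents do not contain.

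The bias argument also stands in part: selection into HVPG is possible. But Follow-up and Record Retention says Velacur gives physicians extra clinical information, so its result might influence whether a recommended procedure goes ahead. Selection on the comparators alone is then only one possibility. Defining analysis sets would not remove such bias. Weighting could help only if patients with and without HVPG overlap on the referral markers, which the documents do not show.

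**Conclusion.** No change to the plan follows. This is missing detail that analysts would fill sensibly: CSPH in patients with HVPG in the window, varices in patients with a completed endoscopy, and Velacur against each marker in patients who have both markers and the reference result. The total of up to 200 is an enrolment ceiling, not a stated CSPH sample, and no power or precision claim depends on it.

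The cost of the gap is that precision cannot be read from the plan. It could be a half-width of 0.061 with 200 verified patients or 0.124 with 50, assuming AUC 0.80 and 50% CSPH; the reported interval will show which. The shift from referral is below 0.01 if referral varies steadily with a comparator, and otherwise cannot be sized or signed from the documents. The conclusion rests on the reading that the ±6 month window covers procedures after the scan and that their results are taken from the records. A sensible report will give the number verified for each target and describe the CSPH result as applying to patients with HVPG.
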